3.2.1.3 FOLFOX as First Line Therapy

FOLFOX have been established as SOC 1L and 2L chemotherapy options for mCRC; however, FOLFOX is more frequently used in the 1L setting. Oxaliplatin combined with infusional 5-FU and leucovorin administered Q2W (FOLFOX) has been shown to be effective [Tournigand, C., et al 2004] and the mFOLFOX7 regimen is considered one of the SOC regimens for 1L treatment of mCRC [National Comprehensive Cancer Network 2017].

The most common AE overall was PSN (76.0%), followed by fatigue (70.9%), nausea (63.7%), diarrhea (53.6%), constipation (39.7%), and vomiting (31.3%); other AEs occurred in $<$ 30% of subjects. The most common SAE was neutropenia (16.7%), PSN (11.1%), diarrhea (8.3%), lymphopenia (2.8%), hypertension (2.8%), vomiting (2.8%), and fatigue (2.8%) [Hochster, H. S., et al 2014]. Neutropenia/neutropenic fever is a known toxicity associated with mFOLFOX6 chemotherapy and may be related to the 5-FU bolus for this regimen, which is known to be associated with myelosuppression. Hochster et al. reported 18.2% Grade 3/4 neutropenia with mFOLFOX7 (without 5-FU bolus), while FOLFOX regimens that contain 5-FU bolus reported significantly higher frequency of approximately 44% to 47% [Hochster, H. S., et al 2014] [Cassidy, J., et al 2011] [Douillard, J. Y., et al 2010]. For this reason in KN651, Sponsor elected to use the mFOLFOX7 regimen, which lacks a 5-FU bolus and is associated with less neutropenia than mFOLFOX6.

3.2.1.4 FOLFIRI as Second Line Therapy

FOLFIRI have been established as SOC 1L and 2L chemotherapy options for mCRC. However, FOLFIRI is more frequently used in the 2L setting after oxaliplatin-based 1L therapies. Irinotecan combined with infusional 5-FU and leucovorin administered Q2W (FOLFIRI) has been shown to be more effective than when irinotecan is combined with bolus 5-FU [Fuchs, C. S., et al 2007]. The regimen is considered one of the SOC regimens in 2L mCRC [National Comprehensive Cancer Network 2017] and has also been shown to be effective in previously untreated patients [Bekaii-Saab, T. 2014]. For example, in the randomized Phase II/III FIRIS study comparing FOLFIRI vs irinotecan/S-1 (IRIS) in 2L

treatment of mCRC, FOLFIRI was associated with ORR of 16.7% and median PFS of 5.1 months. The incidence of Grade 3 or 4 neutropenia was 52.1%. The most common non-hematological toxicities were diarrhea (4.7%), anorexia (5.2%), nausea (4.3%), fatigue (3.3%), and febrile neutropenia (0.9%), all at Grade 3. One treatment-related death from hypotension due to shock was reported in the FOLFIRI group within 28 days after the end of treatment [Muro, K., et al 2010].

3.3 Benefit/Risk Assessment

Participants in clinical trials generally cannot expect to receive direct benefit from treatment/vaccination during participation, as clinical trials are designed to provide information about the safety and effectiveness of an investigational medicine.

Additional details regarding specific benefits and risks for participants participating in this clinical trial may be found in the accompanying binimetinib and pembrolizumab IB, in the respective product labeling for SOC chemotherapy, and in the Informed Consent documents.

Given the unmet medical need that exists for patients with mCRC, described in Section 3.1, the objective of the current trial is to assess safety and tolerability of 5 different novel combinations that includes pembrolizumab. Extended duration of clinical benefit coupled with favorable tolerability and toxicity have been the hallmark of pembrolizumab in many tumor types including MSI-H/pMMR mCRC. Combination regimens being examined in the current trial have a potential to provide improvement of efficacy without increase of toxicity.

3.3.1 Potential Overlapping Toxicities

The combination of pembrolizumab with binimetinib and/or chemotherapy proposed in this protocol potentially may increase overlapping toxicities, and the potential overlapping toxicities for each cohort is presented in [Table 1](#). The most likely overlapping toxicities are described in detail below.

Table 1 Potential Overlapping Toxicities for Each Cohort

Adverse Event	Pembrolizumab +				
	Binimetinib	mFOLFOX7	mFOLFOX7 + Binimetinib	FOLFIRI	FOLRIRI + Binimetinib
Diarrhea	✓	✓	✓	✓	✓
Nausea	✓		✓		✓
Vomiting	✓	✓	✓	✓	✓
Neutropenia		✓	✓		
Peripheral sensory neuropathy		✓	✓		
Rash	✓		✓		✓
Ocular toxicity	✓		✓		✓
Liver test abnormalities	✓		✓		✓
Pneumonitis	✓		✓		✓

Sections 5.4.1.3, 6.2, 7.2.1, 9.3, and 12.5 provide guidance, requirements, and mitigation strategies to minimize the possibility of overlapping toxicities.

3.3.1.1 Pneumonitis

In pooled studies of pembrolizumab, all grade pneumonitis as irAE was reported in 3.4% patients (among which 0.1% were Grade 5), and it is the most frequently reported SAEs considered drug-related by the investigator was pneumonitis (1.6%). In the pooled studies of single-agent binimetinib in patients with advanced cancer (N = 566), pneumonitis events were observed in 15 (2.7%) patients. No individual preferred term was reported for >1.0% of patients, and pneumonitis was the most common event (0.9%). Grade 3/4 pneumonitis events were reported for 4 (0.7%) patients, including pneumonitis, hypoxia, interstitial lung disease, and wheezing. Pneumonitis events were SAEs for 5 (0.9%) patients and resulted in binimetinib discontinuation for 2 (0.4%) patients (MEK162 IB Version 14). Thus, combining pembrolizumab and binimetinib may increase incidence or severity of pneumonitis in participants to be treated in Cohort A. Rare cases of pulmonary toxicities including pneumonitis, organizing pneumonia, pulmonary fibrosis, and interstitial lung disease have been reported with FOLFOX or FOLFIRI treatment [Lee, Y. J. 2014] [Moskovitz, M. 2015] [Katsuta, E. 2011]. Thus, early recognition of pneumonitis and initiation of systemic corticosteroids is critical to reduce the risk of complications.

3.3.1.2 Liver Test Abnormalities

In pooled studies of pembrolizumab, Grade 2-4 hepatitis as irAE was reported in 0.7% patients. Autoimmune hepatitis is the fifth most frequently reported SAEs (0.3%) considered drug-related by the investigator (pembrolizumab current IB). In the pooled studies of single-agent binimetinib in patients with advanced cancer (N = 566), incidence of AST increased and ALT increased were 14.8% and 10.8%, respectively. Grade 3/4 liver events were reported for 6.9% of subjects, including AST increased (3.0%), ALT increased (2.3%), gamma glutamyl transferase increased (1.6%), INR increased (0.7%), ascites (0.5%), blood bilirubin increased and hyperbilirubinemia (0.4% each), and acute hepatic failure, hepatic failure, hepatic function abnormal, hepatic pain and liver injury (0.2% each; binimetinib IB). On the other hand, 5-FU, a thymidylate synthetase inhibitor, when given intravenously, is not only converted in tissues to its active form, 5-fluoro-deoxyuridine-monophosphate, but also catabolized, primarily in the liver, by the dihydrouracil dehydrogenase and then cleaved to α -fluoro- β -alanine, ammonia, urea and carbon dioxide, as in the degradation of uracil. In spite of this well-known liver-mediated catabolism, only mild hepatotoxicity and steatosis have been reported when the drug is given intravenously [Peppercorn, P. D. 1998]. The active metabolite of irinotecan, SN-38, is inactivated by glucuronidation in the liver and can lead to steatosis [Robinson, S. M., et al 2012]. Thus, combination of 5-FU with irinotecan potentially can cause overlapping liver toxicity; however, it is not a common AE associated with FOLFIRI in CRC patients [Vincenzi, B., et al 2015] [Peeters, M. 2015]. In summary, liver test abnormalities or liver toxicities may occur as potential overlapping toxicity in any of the drug combinations proposed in this study, and will be closely monitored. For suspected autoimmune hepatitis, investigators are required to treat with systemic corticosteroids per **Table 6** of the protocol, as specified in protocol Section 7.2.1.2, in addition to appropriate diagnostic tests and supportive care.

3.3.1.3 Diarrhea

Diarrhea is a common AE related to mFOLFOX7, FOLFIRI, binimatinib, and pembrolizumab. In addition, colitis and diarrhea reported as drug-related SAE by the investigator were 0.9%, and 0.6%, respectively, in patients treated with pembrolizumab. The incidence of diarrhea may increase in any of these drug combinations. Thus, all diarrhea events will be closely monitored. For suspected immune related colitis, investigators are required to adequately evaluate and confirm etiology or exclude other causes, and treat with systemic corticosteroids per [Table 6](#) of the protocol, as specified in protocol Section 7.2.1.2. Additional procedures or tests such as colonoscopy and biopsy may be included as part of the evaluation. Supportive care is outlined in Section 7.7.1 and [Table 8](#) of the protocol.

3.3.2 Other Risks

The addition of pembrolizumab and binimatinib may cause toxicities that require dose reduction, interruption and or discontinuation of the approved drugs (mFOLFOX7/FOLFIRI) which have been demonstrated to provide benefit to participants.

4. Objectives/Hypotheses and Endpoints

The objectives and endpoints apply to the study population of adult male and female participants with non-MSI-H/pMMR mCRC.

Objective/Hypothesis	Endpoint
Primary	
Objectives: 
• To determine the safety and tolerability and to establish a preliminary RP2D for the following cohorts:
○ Cohort A: (pembrolizumab in combination with binimatinib in mCRC participants previously treated with fluoropyrimidine, irinotecan, and oxaliplatin).○ Cohort B: (pembrolizumab in combination with mFOLFOX7 in previously untreated mCRC participants)○ Cohort C: (pembrolizumab in combination with mFOLFOX7 and binimatinib in previously untreated mCRC participants).• Determined by incidence of DLTs	

Objective/Hypothesis	Endpoint

 ○ Cohort D: (pembrolizumab in combination with FOLFIRI in mCRC participants previously treated with one line of a fluoropyrimidine plus oxaliplatin-based regimen). ○ Cohort E: (pembrolizumab in combination with FOLFIRI and binimetinib in mCRC participants previously treated with one line of fluoropyrimidine plus oxaliplatin-based regimen) 	
Secondary	

 • To evaluate the ORR based on RECIST 1.1 as assessed by the investigator for each cohort 	
 • (ORR, defined as the proportion of participants in the analysis population who experience CR or PR as assessed by the investigator based on RECIST Version 1.1.
Tertiary/Exploratory	

 • To evaluate serum levels of protein biomarkers (eg, CEA) before and after administration of pembrolizumab in combination with chemotherapy and/or binimetinib for each cohort 	
 • Determination of molecular/proteomic markers indicative of clinical response, safety or mechanism of action of pembrolizumab and other study treatments

 • To evaluate the DOR, DCR, PFS based on RECIST 1.1 as assessed by the investigator and OS for each cohort 	
 • DOR, defined as the time from first documented evidence of CR or PR until disease progression or death due to any cause, whichever occurs first, as assessed by the investigator per RECIST 1.1 criteria. • DCR, defined as and the percentage of participants who have achieved CR or PR or have demonstrated SD prior to any evidence of progression as assessed by the investigator per RECIST 1.1 criteria. • PFS, defined as the time from allocation to the first documented disease progression or death due to any cause, whichever occurs first, as assessed by the investigator based on RECIST Version 1.1 • OS, defined as the time from the date of allocation to the date of death due to any cause.

Objective/Hypothesis	Endpoint

• To evaluate the DOR, ORR, DCR, and PFS based on iRECIST as assessed by the investigator for each cohort	
• DOR, ORR, DCR, and PFS as assessed by the investigator per iRECIST 1.1 criteria

• To identify molecular (genomic, metabolic and/or proteomic) biomarkers that may be indicative of clinical response/resistance, safety, pharmacodynamic activity, and/or the mechanism of action of pembrolizumab in combination with chemotherapy and/or binimetinib for each cohort	
• Germline genetic variation, genetic (DNA) mutations from tumor, tumor and blood RNA variation, proteomics and IHC, and other blood-derived biomarkers• Tumor RNA immune cell activation and MHC molecule expression, proteomics and IHC to assess immune cells (CD8 T cell) infiltration, proliferation, and activation

• To explore the effects of binimetinib on the pharmacokinetics of irinotecan and SN-38, conversely, to estimate the effects of irinotecan and SN-38 on the PK of binimetinib for participants in Cohort A, D, and E	
• Blood samples of binimetinib, irinotecan and SN-38 will be obtained to measure PK of binimetinib, irinotecan, and SN-38, and appropriate methods will be applied to assess the PK interactions.

5. Study Design

5.1 Overall Design

This is a multicenter, worldwide, open label, non-randomized, Phase 1b trial of pembrolizumab in combination with chemotherapy and/or MEK inhibitor binimetinib in participants with a histologically confirmed diagnosis of mCRC (Stage IV) that are non-MSI-H or pMMR. This trial includes 2 parts: Part 1 will be a dose finding phase and Part 2 will be a dose confirmation phase to further examine safety and explore efficacy. There are a total of 5 cohorts. Each of the 5 cohorts will participate in Part 1 and Part 2. The study will evaluate safety, tolerability and efficacy in the following 5 cohorts that will enroll participant with non-MSI-H/pMMR mCRC:

- Cohort A: Pembrolizumab in combination with binimetinib in mCRC participants previously treated with fluoropyrimidine, irinotecan, and oxaliplatin
- Cohort B: Pembrolizumab in combination with mFOLFOX7 in previously untreated mCRC participants
- Cohort C: Pembrolizumab in combination with mFOLFOX7 and binimetinib in previously untreated mCRC participants
- Cohort D: Pembrolizumab in combination with FOLFIRI in mCRC participants previously treated with one line of a fluoropyrimidine plus oxaliplatin-based regimen

- Cohort E: Pembrolizumab in combination with FOLFIRI and binimatinib in mCRC participants previously treated with one line of fluoropyrimidine plus oxaliplatin-based regimen

There is no intent to compare Cohorts B and C or Cohorts D and E. Each cohort will have independent objectives and will be analyzed separately.

The MSI or MMR status must be known prior to enrollment and the participants must be non MSI-H (or pMMR). Local documentation of non MSI-H/pMMR status using one method ie, IHC or PCR will be sufficient to meet eligibility criteria, as defined in Section 5.4.1.6 to be eligible for this study.

Pre-treatment tumor tissue is required to be provided prior to allocation into the study. If not available, a tumor biopsy must be obtained prior to entry in the study.

In both parts of the trial, participants will be allocated using an IVRS/IWRS. Pembrolizumab (200 mg) will be administered by IV infusion on Day 1 of each 21-day cycle; the dose of pembrolizumab will remain constant for all cohorts. Chemotherapy (mFOLFOX7 and FOLFIRI) will be administered by IV infusion every 14 days. Binimatinib will be administered orally BID. For additional details on study treatment administration, please see Section 7.1.

5.1.1 Study Design

5.1.1.1 Part 1 (Dose Finding)

An mTPI design [Ji Y, Li Y, Bekele BN 2007] with a target DLT rate of approximately 30% will be applied to identify a preliminary RP2D in each cohort.

Dose escalation and de-escalation decisions are based on the mTPI design as outlined in [Table 1](#).

For **Cohort A**, the DLT observation period is the first **21-days** of Cycle 1 and the next dose level may open for enrollment once the 21-days DLT observation period of the previous dose is completed and a dose escalation decision is made.

For **Cohorts B, C, D, and E**, the DLT observation period is the first **28-days** to accommodate the chemotherapy schedule and the next dose level may open for enrollment once the 28-days DLT observation period of the previous dose is completed and a dose decision (escalation or de-escalation) is made.

During dose finding, a minimum of 3 participants are required at each dose level, and up to 6 participants may be enrolled in the same cycle at each new dose. In [Table 2](#), the columns indicate the numbers of participants treated at the current dose level, and the rows indicate the numbers of participants experiencing DLT. The entries in the table are the dose-finding decisions: E, S, D, and DU represent escalating the dose, staying at the same dose, de-escalating the dose, and excluding the dose from the trial due to unacceptable toxicity, respectively.

Based on the mTPI design, the number of participants who are enrolled at a dose but are not yet fully evaluable for DLT assessment may not exceed the number of remaining participants who are at risk of developing a DLT before the dose would be considered unacceptably toxic

([Table 2](#)). For example, if 1 out of 3 participants at a given dose level experiences a DLT, no more than an additional 3 participants may be enrolled at this dose level until additional DLT data are available since this dose would be considered unacceptably toxic if all 3 of the additional participants experience a DLT (ie, 4 out of 6 participants). New participants will be enrolled to the next dose level based on the decision as outlined in the mTPI design (see [Table 2](#)). There will be no intra-participant dose level escalation or dose level de-escalation for participants enrolled in this study (ie, 1 participant will be assigned to 1 dose level of the study drug). The definition of DLTs and the criteria for dose modification are outlined in Sections 5.1.3 and 7.2, respectively. The dose with an estimated DLT rate closest to 30% may be treated as a preliminary RP2D. Based on the emerging safety and/or efficacy signals, an alternate dose level may be explored.

The totality of the data will be considered before deciding on the dose(s) to carry forward to Part 2.

[figure not shown]
CCI

Treatment allocation will be accomplished by non-random assignment. If a participant meets the eligibility criteria for Cohorts B and C (i.e., previously untreated) or Cohorts D and E (i.e., previously treated with one line of fluoropyrimidine-based therapy) then IVRS/IWRS will alternate assignments between the 2 cohorts with the same eligibility criteria. Treatment for each cohort in Part 2 will begin once a preliminary RP2D for that cohort is identified in Part 1.

5.1.1.2 Cohort A: Pembrolizumab plus Binimetinib (Participants Previously Treated with Fluoropyrimidine, Irinotecan, and Oxaliplatin)

The dose of pembrolizumab will remain constant at 200 mg Q3W (see Section 5.5.1.1.1). Two dose levels of binimetinib will be explored: 30 mg BID and 45 mg BID. The starting dose of binimetinib will be 30 mg BID and is described in Section 5.5.1.1.2. The dose level of binimetinib will be escalated to 45 mg BID, based upon the mTPI design rules, as outlined in Section 5.1.1.

[figure not shown]

Abbreviations: DL = dose level; 5-FU = fluorouracil; mTPI = modified toxicity probability interval; RP2D = recommended Phase 2 dose; Q3W = every 3 weeks.

Figure 1 Study Diagram (Cohort A)

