10.6.2 Statistical Methods for Safety Analysis

Safety and tolerability will be assessed by clinical review of all relevant parameters including AEs, SAEs, ECIs, laboratory tests, vital signs, ECG measurements, and physical examinations.

[figure not shown]
Adverse events will be summarized by counts and frequencies for each dose level. Laboratory tests, vital signs, and other safety endpoints will be summarized as appropriate.

For Part 1 in each cohort: DLTs will be listed, and further summarized by dose level. The estimates of the DLT rates among participants treated at the RP2D and the 80% Bayesian credible intervals based on a prior distribution of Beta (1,1) for the estimates will be provided.

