10.9 Sample Size and Power Calculations

For each of the combinations, for Part 1 – dose finding phase: With sample size capped at 14 in each dose level, the maximum sample size in Part 1 is expected to be approximately 28 evaluable participants. In Part 2 – dose confirmation phase, approximately 16 additional participants per cohort will be treated at the RP2D identified in Part 1 to bring the total number of evaluable participants in Part 1 and Part 2 treated at RP2D to approximately 30 for each cohort. The actual sample size depends on the safety profiles and number of doses to be studied. A target sample size of 159 participants will be used for trial planning purposes. The key efficacy endpoint will be ORR based on the investigator assessment per RECIST 1.1. [Table 12](#) shows the ORR estimate and 95% CI (Clopper-Pearson interval) in each cohort.

Table 12 Estimate and 95% Confidence Interval of Objective Response Rate in Each Cohort

CCI

Abbreviations: CI=confidence interval; CR=complete response; ORR=objective response rate; PR=partial response.

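### The default RP2D criterion (estimated DLT rate closest to 30%) imposes no dose order and names no estimator, so it can name the lower level after the higher level ended with an escalate or stay decision

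*Combined protocol and SAP*

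**What the plan says.** Section 5.1.1.1 uses an mTPI design "with a target DLT rate of approximately 30% will be applied to identify a preliminary RP2D in each cohort". It then gives the selection criterion: "The dose with an estimated DLT rate closest to 30% may be treated as a preliminary RP2D". Two sentences loosen it: "Based on the emerging safety and/or efficacy signals, an alternate dose level may be explored" and "The totality of the data will be considered before deciding on the dose(s) to carry forward to Part 2".

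On numbers, "a minimum of 3 participants are required at each dose level" and up to 6 may be enrolled together at a new dose. Section 10.9 adds the upper limit: "With sample size capped at 14 in each dose level". Sections 5.1.1.7 and 10.9 then add about 16 participants per cohort in Part 2, to reach about 30 at the RP2D.

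The only model named for DLT rates is in Section 10.6.2 (and the summary in 10.1), which plans "the 80% Bayesian credible intervals based on a prior distribution of Beta (1,1) for the estimates". That applies to participants treated at the RP2D, so after the choice has been made. It does not say whether the point estimate is a posterior mean or median.

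The readable text gives no order constraint across dose levels, no estimator for the selection step and no tie rule. Table 2 is redacted; the text describes it as a grid of escalate, stay, de-escalate and exclude decisions.

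**The concern.** Distance from 30% is a sensible criterion when estimated toxicity rises with dose. Here nothing makes it rise. The lower level may rest on 3 to 6 participants and the higher on 14, so chance alone can put the lower level's estimate above the higher one's and hence nearer to 30%. A Beta(1,1) mean adds to this, because it pulls small samples towards 50%. The criterion can then name the level that mTPI had already escalated from, while the last decision at the higher level was escalate or stay.

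Because the estimator is open, the same counts can also give two answers, and the trial is open-label, so the choice could be made after the data are seen.

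The preliminary RP2D is part of the primary objective. It sets the Part 2 dose for about 16 more participants per cohort, the set for the ORR estimate (10.6.1) and the futility set (10.1). The Cohort B and D results also fix the chemotherapy doses carried into C and E.

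**Working it through.** **Inputs from the documents.** Target 30%; groups of 3 to 6 (5.1.1.1); cap of 14 per level and 16 added in Part 2 (10.9); 4 DLTs in 6 is unacceptably toxic (the example in 5.1.1.1).

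**Assumptions, because Table 2 is redacted.** Beta(1,1) prior for the mTPI decisions, equivalence interval 25% to 35%, exclusion if P(rate > 30%) exceeds 0.95, Part 1 stops when the current level reaches 14.

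**Step 1: reproduce the plan's figures.** At 4/6 the posterior is Beta(5,3) and P(rate > 0.30) = 0.971, which exceeds 0.95, so the level is excluded. At 3/6 it is 0.874, so it is not. This agrees with the protocol's example. The maximum size also agrees: 5 × (2 × 14 + 16) = 220.

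**Step 2: count pairs.** Observed rate = x/n; Beta(1,1) mean = (x+1)/(n+2); the level with the smaller distance from 30% is named.

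| Lower, higher | mTPI decisions | Observed rates | Named | Beta(1,1) means | Named |
|---|---|---|---|---|---|
| 1/6, 1/14 | escalate, escalate | 16.7%, 7.1% | lower | 2/8 = 25%, 2/16 = 12.5% | lower |
| 0/3, 1/14 | escalate, escalate | 0%, 7.1% | higher | 1/5 = 20%, 2/16 = 12.5% | lower |
| 0/3, 0/14 | escalate, escalate | 0%, 0% | tie | 1/5 = 20%, 1/16 = 6.3% | lower |
| 0/3, 3/14 | escalate, stay | 0%, 21.4% | higher | 1/5 = 20%, 4/16 = 25% | higher |

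The first row shows that naming an estimator is not enough. The second shows that the estimator can decide the answer. The last shows that it does not always. A narrower interval (30% ± 3 points) gives the same decisions. These examples need no assumed true DLT rates.

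**Step 3: frequency.** Two levels starting at the lower one, ties counted for the higher level. The lower-named columns give the share of all simulated cohorts in which the lower level is named although the higher level's decision is escalate or stay; the last column gives how often the two estimators name different levels.

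| True rates | Group size | Lower named, observed rates | Lower named, Beta(1,1) means | Estimators disagree |
|---|---|---|---|---|
| 5%, 10% | 3 | 11% | 83% | 72% |
| 10%, 15% | 3 | 14% | 62% | 48% |
| 10%, 20% | 3 | 10% | 45% | 35% |
| 5%, 10% | 6 | 21% | 38% | 17% |
| 10%, 15% | 6 | 26% | 33% | 7% |
| 10%, 20% | 6 | 18% | 24% | 6% |

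Extending the true rates to 15%/25% gives these ranges:

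- Observed rates: about 7% to 14% (groups of 3) or 12% to 26% (groups of 6).
- Beta(1,1) means: about 30% to 83% or 22% to 38%.
- Disagreement: about 23% to 72% or 6% to 17%.

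**Step 4: with an order constraint.** Pooling adjacent violators on observed proportions turns 1/6 and 1/14 into 2/20 = 10% at both levels. With pooled ties counted for the higher level, purely as an illustration, the lower level is named in 0% of these cohorts.

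**Step 5: consistency with the sample size.** 14 + 16 = 30 at the RP2D. A level left at 3 reaches 3 + 16 = 19; one left at 6 reaches 6 + 16 = 22.

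**The case against.** The strongest reply is that the sentence is permissive. It says the dose may be treated as a preliminary RP2D, an alternate level may be explored, and all the data will be weighed. Section 5.1.2 leaves decisions to enroll at the next dose level to the sponsor in consultation with the investigators. Section 5.3.1 describes the aim as the maximum safe and well-tolerated dose, and Sections 5.1.1.1 and 5.1.1.7 say mTPI identifies the dose. This stands: a reader might infer that the plan will carry the lower level into Part 2, and the documents do not support that. The reply does not repair the criterion, which conflicts with those same passages when it names a level that mTPI had moved past.

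A reader might also take Beta(1,1) as the selector and quote the 83%, 62% and 45% figures alone. Section 10.6.2 does not say so, and those figures also need groups of 3. With groups of 6 they fall to 38%, 33% and 24%, and disagreement between estimators falls to 17%, 7% and 6%. The order effect remains: with observed rates it rises to 21%, 26% and 18%.

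A third inference is that Cohorts B and D are equally exposed. They start at DL1, and DL-1 opens only on a de-escalation decision. Simulation of that path with Beta(1,1) means gives 0.7% to 1.7% of cohorts (groups of 3) or at most 0.2% (groups of 6).

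Finally, a note under the redacted Table 2 could name an estimator or an order rule. That cannot be excluded.

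**Conclusion.** The point holds in a limited form. The only numerical RP2D criterion in the readable text ignores dose order and leaves the estimator open. On reachable counts it can name the lower level after an escalate or stay decision at the higher level, and for some counts, not all, the estimator decides which level is named.

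The order effect appears under either estimator and either group size: about 7% to 26% of cohorts with observed rates and about 22% to 83% with Beta(1,1) means. These frequencies rest on the assumed 25% to 35% interval, the 0.95 cut-off, the stop at 14 and true rates from 5%/10% to 15%/25%. The count pairs need no assumed true rates, though their mTPI decisions use the assumed interval.

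This is a faulty default that the plan's discretion can override, not a demonstrated wrong dose. It matters mainly for Cohorts A, C and E. The criterion also sits badly with the plan's expectation of 14 Part 1 participants at the RP2D. It should be corrected, but it does not invalidate the design.

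**What to change.** In Section 5.1.1.1:

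- State that DLT rates by dose level are estimated by isotonic regression (pool-adjacent-violators), and name the input estimate, for example observed proportions, before data are seen.
- Restrict the candidate to levels whose final Table 2 decision is not de-escalate or exclude.
- Have the sponsor prespecify how levels pooled to the same estimate are resolved.
- Reconcile the sentence with the statements that mTPI identifies the dose (5.1.1.1, 5.1.1.7), with the aim in 5.3.1, and with the 14 + 16 = 30 count in 10.9.

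Keep the sentence on the totality of the data, so that the result stays a statistical candidate. Which dose to carry forward, and which way ties go, remains for the sponsor to decide. If the redacted Table 2 already contains such a rule, a cross-reference is enough for that part.

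The cost is a few sentences, with no added participants, visits or data. The small downside is slightly less freedom in naming the statistical candidate.
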